4.7.3 Additional safety assessments

4.7.3.1 Laboratory variables, vital signs and electrocardiograms (ECGs)

The following routine laboratory variables (performed by local laboratories) and vital signs variables will be analyzed. Electrocardiogram (ECG), performed only at screening visit, will not be summarized. Left ventricular ejection fraction (LVEF) collected in the screening echocardiography will be summarized in the baseline characteristics table.

- Hematology:
 - Red blood cells and platelets and coagulation: hemoglobin, hematocrit, red blood cell count (erythrocytes), platelet count, prothrombin time (expressed as international normalized ratio)
 - White blood cells: neutrophils, lymphocytes, monocytes, basophils, eosinophils
- Clinical chemistry:
 - Metabolism: glucose (fasting), HbA1c*, total protein, albumin
 - Electrolytes: sodium, potassium, chloride, calcium, phosphorus, bicarbonate, magnesium
 - Renal function: creatinine*, urea, blood urea nitrogen (BUN), uric acid*, eGFR (MDRD equation)*
 - Liver function*: alanine aminotransferase, aspartate aminotransferase, alkaline phosphatase, lactate dehydrogenase, total and direct bilirubin
 - Hepatitis screen: hepatitis B surface antigen, anti-hepatitis-C antibody
 - Parathyroid hormone (intact)
- Vital signs: heart rate, systolic and diastolic blood pressure, as well as, weight, respiratory rate, and body temperature (and route)

Data below the lower limit of quantification limit (LLOQ) will be replaced by half of the LLOQ, data above the upper limit of quantification (ULOQ) will be replaced by ULOQ value.

For hematological parameters and some selected biochemistry parameters, Sanofi sponsor generic ranges [lower limit of normal (LLN), upper limit of normal (ULN)] are defined and will be used for grading (see list of parameters in [Section 5.4.5](#)). For other biochemistry parameters (noted with * in laboratory variable list above), grading will be derived using local laboratory normal ranges.

For serology and viral load parameters, results may be summarized via shift tables at baseline and at participant's worst post-baseline visit.

Analyses according to PCSA and NCI grading

For laboratory variables, analyses according to NCI grading will be made based on NCI-CTCAE version specified in the protocol. For laboratory variables for which NCI-CTCAE scale is not applicable, potentially clinically significant abnormality (PCSA) summaries may be performed using sponsor or local laboratory normal ranges.

In addition, for vital signs (ie, heart rate, systolic and diastolic blood pressure), PCSA analyses will be performed based on the PCSA criteria listed below.

Vital signs parameter	PCSA criteria
Systolic Blood Pressure (mmHg)	≤ 95 mmHg and decrease from baseline ≥ 20 mmHg ≥ 160 mmHg and increase from baseline ≥ 20 mmHg
Diastolic Blood Pressure (mmHg)	≤ 45 mmHg and decrease from baseline ≥ 10 mmHg ≥ 110 mmHg and increase from baseline ≥ 10 mmHg
Heart Rate (beats/min)	≤ 50 beats/min and decrease from baseline ≥ 20 beats/min ≥ 120 beats/min and increase from baseline ≥ 20 beats/min

Analyses according to PCSA and NCI grading will be performed based on the worst value during the treatment-emergent period, using all measurements (either local or central, either scheduled, nonscheduled or repeated).

For laboratory variables and vital signs above, the incidence of participants with at least one PCSA during the treatment-emergent period will be summarized regardless of the baseline level and according to the following baseline status categories:

- Normal/missing
- Abnormal according to PCSA criterion or criteria

For laboratory variables graded by NCI-CTCAE,

- The number (%) of participants with abnormal laboratory tests at baseline will be presented by grade.
- The number (%) of participants with abnormal laboratory tests during the treatment-emergent period will be summarized by grade. When appropriate, the number (%) of participants with abnormality of any grade and with Grade 3-4 abnormalities will be provided.

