9.4.2 Safety analyses

All safety analyses will be performed on the Safety Evaluable Population for Phase 1 and All Treated Population for Phase 2.

For safety analyses, the observation period will be divided into 3 segments:

- The pretreatment period is defined as the time from when the participants give informed consent to the first administration of the IMP.

- The on-treatment period is defined as the time from the first dose of IMP up to 30 days after the last dose of IMP.
- The post-treatment period is defined as the time starting 31 days after the last dose of IMP to study cut-off.

Analyses of adverse events

Adverse events will be coded according to Medical Dictionary for Regulatory Activities (MedDRA) and graded according to NCI-CTCAE (version 5.0 criteria).

An overall summary of TEAEs will be provided. The number (%) of participants experiencing TEAEs by primary system organ class (SOC) and preferred term (PT) will be summarized by CTCAE grade (all grades and Grade ≥ 3). Similar summary tables will be generated for treatment related TEAEs, AESIs, TEAEs leading to treatment discontinuation, serious TEAEs, and TEAEs with fatal outcome. Post-treatment AEs will be analyzed separately.

Clinical laboratory evaluations

All laboratory abnormalities will be graded according to NCI-CTCAE, when applicable. The number (%) of participants with laboratory abnormalities (ie, all grades and grade ≥ 3) will be tabulated using the worst grade during on-treatment period.

Table 10 - Safety analyses

Endpoint	Statistical Analysis Methods
Primary: AEs/SAEs, and laboratory abnormalities in Phase 1	Will be listed
Secondary: AEs/SAEs, and laboratory abnormalities in Phase 2	Will be summarized using descriptive statistics
Exploratory	Not applicable

Abbreviations: AE = adverse event, SAE = serious adverse event

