5.4.5 Generic ranges for hematological and biochemistry parameters

Table 12 - Generic ranges for hematological parameters

Test	Gender	Unit	Lower/Upper limit of normal
Hemoglobin	F	g/L	120 - 160
Hemoglobin	M	g/L	135 - 175
Lymphocytes		10 ⁹ /L	1 - 2
Neutrophils		10 ⁹ /L	1.8 - 3.15
Platelets		10 ⁹ /L	150 - 350
Leukocytes		10 ⁹ /L	4.5 - 11
Eosinophils		10 ⁹ /L	0 - 0.4
Basophils		10 ⁹ /L	0 - 0.15
Monocytes		10 ⁹ /L	0.18 - 0.5
Hematocrit	M	Ratio	0.41 - 0.53
Hematocrit	F	Ratio	0.36 - 0.46
Erythrocytes	F	10 ¹² /L	4 - 5.2
Erythrocytes	M	10 ¹² /L	4.5 - 5.9
INR		ratio	0.8 - 1.2

Based on Kratz et al. (4)

Table 13 - Generic ranges for biochemistry parameters

Test	Unit	Lower – Upper limit of normal
Albumin	g/L	35 - 55
BUN	mmol/L	3.6 - 7.1
Calcium	mmol/L	2.2 - 2.6
Chloride	mmol/L	80 - 115
Corrected calcium	mmol/L	2.2 - 2.6
Glucose	mmol/L	3.9 - 7
Bicarbonate (HCO ₃)	mmol/L	22 - 29
Carbon dioxide	mmol/L	21 - 30
Potassium	mmol/L	3.5 - 5
Magnesium	mmol/L	0.8 - 1.2
Sodium	mmol/L	136 - 145
Phosphate	mmol/L	1 - 1.4
Protein	g/L	55 - 80
Urea	mmol/L	3.6 - 7.1

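### SAP Table 12 contradicts itself: the upper limits for the five white-cell types sum to 6.2 ×10⁹/L, but the leukocyte upper limit is 11

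*SAP*

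**What the plan says.** SAP 4.7.3.1 names the white-cell variables to be analyzed: "White blood cells: neutrophils, lymphocytes, monocytes, basophils, eosinophils". Total leukocytes are not in that list, but Table 12 gives a range for them. Protocol Table 11 lists the same five types as the differential of the white count.

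On reference ranges, SAP 4.7.3.1 says that for hematology and selected chemistry tests "Sanofi sponsor generic ranges [lower limit of normal (LLN), upper limit of normal (ULN)] are defined and will be used for grading". Chemistry tests marked with an asterisk are graded from local laboratory ranges instead. No hematology test carries the asterisk.

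On the scale, the SAP says "analyses according to NCI grading will be made based on NCI-CTCAE version specified in the protocol", in line with Protocol 9.4.2: "All laboratory abnormalities will be graded according to NCI-CTCAE, when applicable". For laboratory tests that the scale does not cover, "potentially clinically significant abnormality (PCSA) summaries may be performed using sponsor or local laboratory normal ranges".

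The limits are in SAP 5.4.5, Table 12. One row reads "Lymphocytes 10 ⁹ /L 1 - 2". The other white-cell rows are set out in the working.

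**The concern.** A total count is the sum of its parts. If each part has a ceiling, the total cannot pass the sum of the ceilings unless some part passes its own. Here that sum lies well below the ceiling given for the total, so the table treats a leukocyte count as normal while making it impossible for all its components to be normal.

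These limits are a prespecified input to the laboratory safety tables. A programmer who follows the SAP would load them. Laboratory abnormalities are a primary endpoint in Phase 1 and a secondary one in Phase 2, and the drug targets CD38 on immune cells, so the white-cell tables will be read closely. The analysis takes the worst on-treatment value from all draws, including unscheduled ones, so false highs would accumulate within a participant wherever the limits are applied.

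**Working it through.** The documents state no calculated figure on this point, so there is none to reproduce. The inputs are the Table 12 limits, in 10⁹/L:

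| Type | Lower | Upper | Lower ÷ 4.5 | Upper ÷ 4.5 |
|---|---|---|---|---|
| Neutrophils | 1.8 | 3.15 | 40% | 70% |
| Lymphocytes | 1 | 2 | 22.2% | 44.4% |
| Monocytes | 0.18 | 0.5 | 4% | 11.1% |
| Eosinophils | 0 | 0.4 | 0% | 8.9% |
| Basophils | 0 | 0.15 | 0% | 3.3% |
| Sum of the five | 2.98 | 6.20 | | |
| Leukocytes | 4.5 | 11 | | |

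**Upper limits.** 3.15 + 2 + 0.5 + 0.4 + 0.15 = 6.20, and 6.20/11 = 56%. If all five types are within limits and make up the total, the total is at most 6.20. Any total above 6.20 therefore has at least one type over its limit.

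**Share of the normal range affected.** (11 − 6.2)/(11 − 4.5) = 4.8/6.5 = 73.8%. Only totals from 4.5 to 6.2 (1.7/6.5 = 26.2%) can have all five types within limits.

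**Size of the excess.** The four types other than neutrophils have upper limits that sum to 3.05. At the mid-range total of 7.75, with those four at their upper limits, neutrophils would be 7.75 − 3.05 = 4.70, which is 49% above 3.15. At a total of 11 they would be 7.95, about 2.5 times the limit. Rounding does not explain gaps of this size.

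**Lower limits.** 1.8 + 1 + 0.18 + 0 + 0 = 2.98, below 4.5. A total at or above 4.5 is compatible with every type being at or above its lower limit, so there is no contradiction on that side.

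**Cells outside the five types (assumption).** If a fraction q of cells is unclassified, the threshold becomes 6.2/(1 − q). For q = 5%, 10% and 15% this is 6.53, 6.89 and 7.29, and the affected share of the range is 69%, 63% and 57%.

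**Share of counts rather than of range width (assumption).** The documents give no distribution of leukocyte counts. Taking 4.5 to 11 as a central 95% range, the share of normal totals above 6.2 is 84% (normal distribution) or 72% (log-normal). Keeping the normal SD of 6.5/(2 × 1.96) = 1.66 and moving the center to 7.0, 6.5, 6.0 or 5.5 gives 73%, 64%, 55% or 46%.

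**The case against.** The strongest reply is that an inconsistent table need not produce a wrong result. A reader might infer that most normal white counts must be flagged high. The documents do not support that. A total between 6.2 and 11 is normal in Table 12, so the white count itself is not flagged. Neither document has a rule that flags every value above an upper limit. Grading follows NCI-CTCAE, whose text is not in the documents, and neither document says which white-cell types are graded upward from the upper limit. Outside that scale the PCSA summaries are optional and may use local ranges. All of this stands, and it limits the consequence to analyses that do use the sponsor upper limit.

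A reader might also infer that the Phase 1 safety conclusion or the choice of dose is affected. Pre-defined unacceptable toxicity rests on verified Grade 4 events, and no route is shown from an excess over these upper limits to Grade 4. Nor is it shown that participants would be placed in the wrong baseline stratum. That stratum is defined by PCSA criteria, and the SAP gives numeric criteria only for vital signs.

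It can further be said that ranges for parts need not add up to the range for the whole. That is true, but it does not rescue the table. The five types are seldom all at their upper limits at once, so the component limits would be expected to sum to more than the total's limit, and here they sum to little more than half of it.

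Finally, the cause is not established. Both neutrophil limits are exact round percentages of 4.5, the leukocyte lower limit, and the monocyte lower limit is 4% of it. The remaining nonzero limits are not round percentages of 4.5. The source cited for the table is not available here.

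**Conclusion.** Table 12 is wrong as written on its high side: the five component upper limits and the leukocyte upper limit cannot all hold. The firm size is 74% of the width of the normal leukocyte range. It rests only on the tabulated limits and on the five types making up the total, and it stays above half (57%) if as many as 15% of cells fall outside them. A share of participants or samples cannot be stated. The scenarios tried run from 46% to 84% and depend on an assumed distribution.

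The consequence is conditional. Any white-cell type graded or summarized in the high direction against the sponsor limit, including a PCSA summary run with sponsor ranges, would show false high values. Analyses in the low direction are not touched by this contradiction, and no effect on Grade 4 toxicity, dose decisions or the efficacy endpoint is shown. Scaling of the upper limits from the leukocyte lower limit (1.8 and 3.15 are exactly 40% and 70% of 4.5) is a possible explanation, not a finding.

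**What to change.** Check SAP Table 12 against its source. Then do one of the following:

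- correct the upper limits for neutrophils, lymphocytes, monocytes, eosinophils and basophils so that they are consistent with the leukocyte upper limit of 11; or
- use local laboratory upper limits for these five types, as SAP 4.7.3.1 already does for the starred chemistry tests. Protocol 10.2 has these tests run locally.

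Keep the lower limits. Add a sentence to SAP 4.7.3.1 stating which white-cell types are assessed in the high direction, and against which limit.

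For scale only: with the other four upper limits unchanged, the neutrophil limit would have to be 11 − 3.05 = 7.95 for the five just to reach 11. The values themselves should come from the source and not from this sum.

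The cost is one table correction, one sentence and a lookup change in the grading program, made before database lock. No new data are needed.

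### Baseline status for vital-sign PCSAs is defined by criteria that require a change from baseline, so the abnormal-at-baseline category is empty by construction for blood pressure and heart rate

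*SAP*

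**What the plan says.** SAP section 4.7.3.1 plans PCSA analyses for three vital signs and prints a low and a high criterion for each:

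- Systolic pressure: "≤ 95 mmHg and decrease from baseline ≥ 20 mmHg ≥ 160 mmHg and increase from baseline ≥ 20 mmHg"
- Diastolic pressure: "≤ 45 mmHg and decrease from baseline ≥ 10 mmHg ≥ 110 mmHg and increase from baseline ≥ 10 mmHg"
- Heart rate: "≤ 50 beats/min and decrease from baseline ≥ 20 beats/min ≥ 120 beats/min and increase from baseline ≥ 20 beats/min"

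For laboratory variables and these vital signs, the number of participants with at least one PCSA in the treatment-emergent period "will be summarized regardless of the baseline level and according to the following baseline status categories". The two categories are "Normal/missing" and "Abnormal according to PCSA criterion or criteria".

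SAP section 4.1 defines baseline as the last value available before the first dose. Neither document gives a separate rule for deciding whether a baseline vital sign is abnormal.

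**The concern.** A split by baseline status lets the reader tell an abnormality that arose on treatment from one in a participant who was already outside the limits at entry. For that, the abnormal category must be one that a baseline value can fall into. Here it borrows criteria written for on-treatment values, each of which needs a shift away from baseline.

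At stake is the meaning of one descriptive safety table. The trial has no control arm, so entry status is a natural reference for judging a blood-pressure or heart-rate shift. Vital signs are taken before, one hour into and at the end of each infusion (protocol section 8.2.2). Entry values beyond the limits can occur: exclusion E 03 covers only severe autonomic dysfunction leading to chronic hypotension, and no criterion in protocol sections 5.1 and 5.2 caps blood pressure.

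**Working it through.** The plan states no figure to reproduce. The check is whether any baseline value can satisfy a criterion.

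**Inputs.** Limits and required changes are from the table in SAP 4.7.3.1; the definition of baseline is from SAP 4.1.

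| Vital sign | Low limit | High limit | Required change d |
|---|---|---|---|
| Systolic (mmHg) | 95 | 160 | 20 |
| Diastolic (mmHg) | 45 | 110 | 10 |
| Heart rate (beats/min) | 50 | 120 | 20 |

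**Step 1: the criteria.** With observed value V and baseline B:

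- low PCSA: V ≤ low limit and B − V ≥ d
- high PCSA: V ≥ high limit and V − B ≥ d

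**Step 2: apply them to baseline.** Put V = B. The second condition becomes 0 ≥ d, with d equal to 10 or 20. It is false for every B, so none of the six criteria can be met.

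**Step 3: check by enumeration.** The criteria were coded as printed and evaluated at V = B for every integer in a wide range, then again with the absolute limit alone.

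| Vital sign | Values tested | Abnormal, full criterion | Abnormal, limit alone |
|---|---|---|---|
| Systolic, 50 to 260 | 211 | 0 | 147 |
| Diastolic, 20 to 160 | 141 | 0 | 77 |
| Heart rate, 25 to 220 | 196 | 0 | 127 |

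The last column shows only that the limit alone makes the category fillable. It counts possible values and says nothing about how many participants have them.

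**Step 4: effect on the table.** The abnormal row has denominator 0. The normal-or-missing row therefore has the same participants and the same events as the summary made regardless of baseline.

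**Step 5: individual cases.**

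- Baseline systolic 170, on treatment 192: 192 ≥ 160 and 192 − 170 = 22 ≥ 20, so a high PCSA is counted. At baseline 170 − 170 = 0 < 20, so the event appears in the normal-or-missing row although entry pressure was above the SAP's own limit.
- Baseline systolic 165: same row. A high PCSA needs at least 165 + 20 = 185.
- Baseline systolic 90: also in the normal-or-missing row, although below the low limit of 95.

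**Step 6: direction.** A participant with baseline systolic 90 who reaches 165 has a high PCSA (165 ≥ 160; 165 − 90 = 75 ≥ 20). Entry status was low, not high, so this is a new high abnormality. If baseline status pooled the low and high limits, it would be filed as already abnormal. Baseline status should therefore follow the direction of the criterion.

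**The case against.** **Programmers will apply only the absolute part at baseline.** This is plausible and sensible, but the SAP does not say it. The category refers to the criteria, and the criteria printed are the full conjunctions.

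**The change could be taken against an earlier pre-dose value.** A screening systolic pressure of 140 followed by 165 before the first infusion would meet the high criterion if measured against screening. SAP 4.1 does not allow this, because baseline is the single last pre-dose value.

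**The change condition already does most of the work.** This largely stands. A participant at 170 at entry and 175 on treatment is not counted, because the rise is 5. The 170-to-192 case is a real rise of 22 and should be counted. What remains wrong is the row in which it appears.

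**The effect is small.** This stands. The incidence regardless of baseline and every treatment-emergent PCSA count are unchanged. Laboratory PCSAs rest on normal ranges with no stated change condition, and graded laboratory tables are separate. SAP 4.7 describes the safety analysis as descriptive, without testing.

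A reader might also infer three stronger points that the documents do not support:

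- *That the vital-sign PCSA analysis is uninformative.* Only the split by baseline status is lost; the overall summary remains valid.
- *That a given number of participants is misfiled.* The documents give no distribution of entry blood pressure or heart rate, so any count needs an outside prevalence. Such a count would also measure row assignments, not misplaced events. A misplaced high systolic event needs a baseline of at least 160 and a further rise of at least 20, hence a value of at least 180. The size of that subset is unknown and could be zero.
- *That missing baselines distort the denominator.* Vital signs are scheduled at screening and before every infusion, and SAP 5.4.1 lets unscheduled values count towards baseline, so a missing baseline is unlikely. SAP 5.4.1 also bases percentages on non-missing observations. The pooled label leaves some ambiguity, but not a demonstrated error.

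**Conclusion.** The point holds for systolic pressure, diastolic pressure and heart rate. Followed as written, the rule places 100% of participants in the normal-or-missing category for all three, whatever the data. The abnormal row is empty, the other row duplicates the overall summary, and a participant already beyond a limit at entry is reported alongside those with normal or missing baselines.

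This follows from the printed criteria and the baseline definition alone and needs no assumption about the data. It does assume that the criteria are applied in full at baseline, which is what the text says. The consequence is confined to a descriptive split of three vital signs. The overall PCSA incidence, the laboratory tables and the primary endpoint do not change. It is a minor correction, worth making because the planned output is degenerate and mislabelled.

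**What to change.** Add one sentence to SAP 4.7.3.1: for vital signs, baseline status is determined by the absolute limit of the criterion only, separately for each direction.

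- Low criteria, abnormal at baseline if systolic ≤ 95 mmHg, diastolic ≤ 45 mmHg or heart rate ≤ 50 beats/min, each for its own parameter.
- High criteria, abnormal at baseline if systolic ≥ 160 mmHg, diastolic ≥ 110 mmHg or heart rate ≥ 120 beats/min, each for its own parameter.

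Leave the treatment-emergent PCSA definition, with its change condition, as it is. The limits are already in the SAP. The cost is one sentence and a small programming change, with no new data.

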 - Participants with antiviral therapy for HCV started before initiation of IMP and positive HCV antibodies are eligible. The antiviral therapy for HCV should continue throughout the treatment period until seroconversion. Participants with positive anti-HCV and undetectable HCV ribonucleic acid (RNA) without antiviral therapy for HCV are eligible.

- E 10. Participants with active lupus or uncontrolled diabetes, per Investigator's judgment.

Prior/concomitant therapy

- E 11. Prior treatment with an agent (approved or investigational) that blocks CD38 (patients who had previously participated in a study with an anti-CD38 but have written confirmation they were on control arm are allowed).
- E 12. Prior treatment with biological therapy, major surgery, desensitization therapy, or immunosuppressive therapy (up to 10 mg prednisone/day or equivalent is allowed) within 28 days from initiation of IMP.
- E 13. Recipients of any live attenuated vaccine(s) within 4 weeks of IMP initiation.
- E 14. Received treatment with rituximab or obinutuzumab within 6 months from initiation of IMP.
- E 15. Received prior liver, heart, or lung transplantation.
- E 16. Received cell transplantation or cell therapy within 5 years prior to IMP initiation.

Prior/concurrent clinical study experience

E 17. Prior treatment with any investigational drugs within 28 days from initiation of IMP or concomitant enrollment in any other clinical study involving an investigational study treatment.

Diagnostic assessments

E 18. Inadequate organ and bone marrow function at the Screening Visit:

- Absolute neutrophil count (ANC) $<1500/\text{mm}^3$ ($1.5 \times 10^9/\text{L}$),
- Platelets $<90 \times 10^9/\text{L}$ (platelet transfusion is not allowed within 7 days before the screening hematological test),
- Hemoglobin $<9 \text{ g/dL}$ or $<5.6 \text{ mmol/L}$ (without transfusion 7 days before the screening hematological test),
- Total bilirubin >1.5 upper limit of normal (ULN),
- Aspartate aminotransferase (AST) and/or alanine aminotransferase (ALT) $>3 \times \text{ULN}$,
- Alkaline phosphatase (ALP) $>2.5 \times \text{ULN}$.

Other exclusions

E 19. Pregnant or breastfeeding women or women who intend to become pregnant during participation in the study.

E 20. Known intolerance or hypersensitivity to any component of isatuximab or premedications.

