4.7.2 Adverse events

General common rules for adverse events

All AEs will be graded according to National cancer institute common terminology for adverse events [(NCI-CTCAE) version 5.0] and coded to a lower-level term (LLT), preferred term (PT), high-level term (HLT), high-level group term (HLGT), and associated primary system organ class (SOC) using the Medical Dictionary for Regulatory Activities (MedDRA) version currently in effect at Sanofi at the time of database lock.

The AEs will be analyzed in the following 3 categories:

- Pre-treatment AEs: AEs that developed, worsened or became serious during the pre-treatment period.
- Treatment-emergent adverse events (TEAE)s: AEs that developed, worsened or became serious during the on-treatment period
- Post-treatment AEs: AEs that developed, worsened or became serious during the post-treatment period

Similarly, deaths will be analyzed in the pre-treatment, treatment-emergent and post-treatment periods.

The primary focus of AE reporting will be on TEAEs. Pre-treatment and post-treatment AEs will be described separately.

An AE with incomplete or missing date/time of onset (occurrence, worsening, or becoming serious) will be classified as a TEAE unless there is definitive information to determine it is a pre-treatment or a post-treatment AE.

If the assessment of the relationship to IMP is missing for an AE, this AE will be assumed as related to IMP. If the toxicity grade is missing for 1 of the treatment-emergent occurrences of an AE, the toxicity grade will be imputed with the maximal severity of the other occurrences. If the severity is missing for all the occurrences, the toxicity grade will be left as missing.

Multiple occurrences of the same event in the same participant will be counted only once in the tables within a treatment phase, using the maximum (worst) grade by treatment phase. Summaries will be provided for all grades combined and for grade ≥ 3 (including Grade 5). Missing grades, if any, will be included in the “all grades” category.

The AE tables will be sorted as indicated in [Table 5](#).

Table 5 - Sorting of AE tables

AE presentation	Sorting rules
SOC and PT	By the internationally agreed SOC order and decreasing frequency of PTs ^{a, b}
PT	By decreasing frequency of PTs ^a

a Sorting will be based on the overall incidence.

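### For NCI-graded laboratory tests, baseline grades and worst on-treatment grades are tabulated separately and never crossed, so the planned tables cannot show how many participants worsened

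*SAP*

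**What the plan says.** SAP 4.7.3.1 gives NCI-graded laboratory tests two one-way summaries. The first is the baseline margin: "The number (%) of participants with abnormal laboratory tests at baseline will be presented by grade". The second is the on-treatment margin: "The number (%) of participants with abnormal laboratory tests during the treatment-emergent period will be summarized by grade". The value graded is the worst one: "Analyses according to PCSA and NCI grading will be performed based on the worst value during the treatment-emergent period, using all measurements". Protocol 9.4.2 has the same rule without a baseline condition; laboratory abnormalities are "tabulated using the worst grade during on-treatment period".

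Other safety outputs in the SAP do take each participant's starting point into account:

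- The incidence of potentially clinically significant abnormalities (PCSA), used for vital signs and for laboratory variables without an NCI scale, "will be summarized regardless of the baseline level and according to the following baseline status categories" (normal or missing, and abnormal).
- For serology and viral load, "results may be summarized via shift tables at baseline and at" the worst post-baseline visit. This is optional.
- Treatment-emergent adverse events are defined in SAP 4.7.2 as "AEs that developed, worsened or became serious during the on-treatment period".

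SAP 5.4.1, on unscheduled visits, mentions shift summaries for safety, but no section defines one for graded hematology or chemistry.

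Laboratory abnormalities belong to the Phase 1 primary and the Phase 2 secondary safety endpoints (SAP 1.2).

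**The concern.** Every participant has chronic kidney disease and receives isatuximab. The matched external controls in SAP 5.4.3 and 5.4.4 serve transplantability and transplant outcomes; no laboratory-safety comparison with them is described. Each participant's own baseline is therefore the main reference for laboratory safety.

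Two uncrossed margins use that reference only at group level. They show how many were abnormal before and how many during treatment, but not whether these were the same people or who moved to a worse grade. Some of the affected tests are also ones where the protocol expects a possible effect: section 2.3.3 discusses the risk of neutropenia, and the bulletin in Appendix 10 mentions a fall in hemoglobin of about 1 g/dL with anti-CD38 treatment. At stake is whether the safety summary can say how many participants worsened in these tests.

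**Working it through.** The plan states no figure on this point, so there is none to reproduce. The check compares entry limits with grading limits, then asks what two margins can identify.

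**Step 1. Can participants enter already abnormal?** Protocol 5.2, E 18 ("Inadequate organ and bone marrow function at the Screening Visit") sets the entry limits. SAP Table 12 gives the sponsor ranges that SAP 4.7.3.1 uses for grading hematology.

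| Test | Lowest value allowed at screening | SAP lower limit of normal |
|---|---|---|
| Hemoglobin | 90 g/L (9 g/dL) | 120 g/L (women), 135 g/L (men) |
| Platelets | 90 × 10⁹/L | 150 × 10⁹/L |
| Neutrophils | 1.5 × 10⁹/L | 1.8 × 10⁹/L |

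In all three tests a participant can be eligible and already below normal. E 18 also admits AST/ALT up to 3 × ULN and alkaline phosphatase up to 2.5 × ULN; these are graded on local ranges, not on Table 12.

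**Step 2. What do the two margins identify?** Let n be the number of participants, k0 the number abnormal at baseline and k1 the number abnormal on treatment. The number newly abnormal lies between max(0, k1 − k0) and min(k1, n − k0). Take n = 12, the minimum per cohort (SAP section 2), with assumed counts:

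- k0 = 6, k1 = 6: from max(0, 0) = 0 to min(6, 6) = 6.
- k0 = 6, k1 = 9: from max(0, 3) = 3 to min(9, 6) = 6.
- k0 = 9, k1 = 9: from max(0, 0) = 0 to min(9, 3) = 3.

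The upper ends require some participants abnormal at baseline to be normal at every on-treatment measurement. In the first case all six would have to be. If no baseline abnormality resolves, the newly abnormal number is k1 − k0, the lower end. Even then, worsening among those already abnormal stays hidden: a Grade 2 on treatment may come from Grade 1 or from normal.

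**Step 3. What does the on-treatment table show by itself?** Let b be the baseline prevalence, assumed to persist, and q the true new-onset rate among those normal at baseline. The reported rate is b + (1 − b)q. The documents give neither value, so a range is shown.

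| b | q = 0 | q = 20% |
|---|---|---|
| 25% | 25% | 0.25 + 0.75 × 0.20 = 40% |
| 50% | 50% | 0.50 + 0.50 × 0.20 = 60% |
| 75% | 75% | 0.75 + 0.25 × 0.20 = 80% |
| 90% | 90% | 0.90 + 0.10 × 0.20 = 92% |

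The higher the baseline prevalence, the more the on-treatment rate reflects the starting state. At b = 90%, a new-onset rate of 20% moves it by only 2 percentage points.

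**Step 4. Which grades are affected?** The entry minima for neutrophils (1500/mm³), platelets (90 000/mm³) and hemoglobin (9 g/dL) lie above the levels to which Protocol Table 5 requires recovery after a Grade 4 event (1000/mm³, 50 000/mm³ and 8 g/dL). A Grade 4 value in these three tests would therefore normally be new. The ambiguity sits in the lower grades and in tests without an entry limit, such as lymphocytes.

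**The case against.** The strongest case on the other side is that this is a presentation choice in a descriptive analysis of about 24 to 42 participants, with no testing planned. Several parts of it stand.

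- A reader might infer that the SAP ignores baseline. It does not: the baseline table sits directly before the on-treatment one. If half the participants enter anemic and nobody changes, both tables show 50% and there is no net change to misread. The gap is the missing cross-classification.
- A reader might infer that pre-existing abnormalities are labelled treatment-emergent. The SAP's wording names a time window; its emergence concept is reserved for adverse events.
- A reader might infer that the Phase 1 primary endpoint is distorted. The protocol synopsis and Protocol Table 10 say Phase 1 laboratory abnormalities will be listed. The definition of unacceptable toxicity excludes events due solely to underlying disease, and the dose decision rests on all safety findings together. SAP 4.3.1 does send the Phase 1 laboratory analysis to 4.7.3.1, but a percentage from this table does not drive the decision.
- Clinically significant worsening can also be reported as an adverse event (Protocol Appendix 3). This helps only in part, because findings associated with the underlying disease are not adverse events unless judged more severe than expected. That route depends on investigator judgment; the graded table does not.
- The shift summaries mentioned in SAP 5.4.1 suggest that such output may be intended. They are undefined and may refer only to serology, so the gap remains.

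**Conclusion.** The point holds in a limited form. For NCI-graded laboratory tests, the planned tables count participants already abnormal at entry and do not identify how many newly developed or worsened an abnormality. With 12 participants and assumed counts of 6 and 6, the newly abnormal number could be anything from 0 to 6; with 9 and 9, from 0 to 3. These counts are illustrations, since the documents give no baseline prevalence.

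The effect falls mainly on the All Treated summaries and the Phase 2 secondary safety endpoint. Grade 4 neutropenia, thrombocytopenia and anemia are largely outside it because of the entry limits. The efficacy estimand, alpha, power and sample size are untouched. The documents do not support the stronger conclusion that the safety analysis as a whole cannot tell disease from treatment: adverse event tables and Phase 1 listings give further information. The change is still worth making, because baseline is the main reference available and the SAP already uses it this way for PCSA variables.

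**What to change.** In SAP 4.7.3.1 add, for each NCI-graded laboratory test, a shift table of baseline grade by worst on-treatment grade. From it, report the number (%) of participants who worsen by at least one grade and the number (%) with new Grade 3-4, stating how missing baseline values are handled. State in 5.4.1 that these are among the shift summaries mentioned there.

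The cost is a few extra standard tables from data already collected, with no change to design, visits or sample size. The tables should be described as showing worsening on treatment: without a control arm they cannot attribute that worsening to the drug.
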